8.3 EVALUATION OF RESPONSE

Any patient who is enrolled and receives at least one dose of mithramycin will be considered evaluable for response provided: (1) the patient demonstrates progressive disease or death while on protocol therapy; (2) the patient is observed on protocol therapy for at least one cycle and the tumor is not removed surgically prior to the time complete response or partial response is confirmed; or (3) the patient demonstrates a complete or partial response as confirmed according to protocol criteria. Patients who electively terminate therapy before receiving all 7 doses of mithramycin during the first treatment cycle and do not expire within 28 days from start of treatment will be replaced. Patients who demonstrate a complete or partial response will be considered to have experienced a response. The evaluation period for determination of the best response will be 6 treatment cycles. All other patients will be considered non-responders.

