8.2 PHASE II PORTION

The primary endpoint will be objective response by RECIST criteria v 1.1. The best response of disease to mithramycin will be examined. The following outlines the Simon optimal two stage design that will be used:

	Cumulative Number of Responses	Decision
Stage 1: Enter 9 patients	0	Terminate the trial: agent ineffective
	1 or more	Inconclusive result, continue trial (proceed to Stage 2)
Stage 2: Enter 15 additional patients	2 or fewer	Terminate the trial: agent ineffective
	3 or more	Terminate the trial: agent effective

We will consider mithramycin not of sufficient interest for further evaluation in a disease category if the true response rate is 5% ($p_0=0.05$) and of sufficient activity if the true response rate is 25% ($p_1=0.25$). As summarized in the above table, with $\alpha=0.10$ (10% probability of accepting an ineffective treatment) and $\beta=0.10$ (10% probability of rejecting an effective treatment), the study will initially enroll 9 patients and if 0 of 9 have a response, then no further patients will be enrolled. If 1 or more respond, accrual will continue until a total of 24 evaluable patients have been enrolled. After 24 patients have been enrolled and evaluated, 1-2 with a response will be considered insufficient while if 3 or more respond in 24 patients, this will be considered sufficient activity for further investigation. Under the null hypothesis, the probability of early termination is 63%.

The two patients that were enrolled in the 25 mcg/kg dose of the Phase II portion will be evaluated for response but not be counted as evaluable for the design above, as they received mithramycin at a higher single dose (25 mcg/kg) than the new phase II dose (17.5 mcg/dose) determined with amendment B. The accrual ceiling will be increased by two patients to allow for these non-evaluable patients.

If the pediatric phase II dose of mithramycin determined on this trial differs from the adult phase II dose, the protocol will be amended to address accrual and response rate to mithramycin in children in a separate stratum.

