8.2.1 Methods of Analysis

Patients who are considered evaluable for response will be included in an analysis of time to progression. Time to progression will be estimated using the product-limit method of Kaplan and Meier. The probability of progression free survival at 6 months will be summarized. Response rates will be calculated as the percent of patients whose best response is a CR or PR, and the fraction of responses obtained will have a 95% confidence interval, which takes into consideration the two-stage nature of the design (50). Toxicity information recorded will include the type,

severity, time of onset, time of resolution, and the probable association with the study regimen. Tables will be constructed to summarize the observed incidence by severity and type of toxicity.

Time to progression will be taken as the number of days from enrollment until: (1) disease progression; (2) death because of treatment complications; (3) resection of measurable tumor; or (4) last patient follow-up whichever is first. Patients will be considered to have experienced a progression event if (1) or (2) occurs. Otherwise, the patient will be considered censored for time to progression.

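### Section 8.3 drops patients resected with stable disease or an unconfirmed response from the evaluable set; this can only raise the response rate and leaves the resection-censoring rule in 8.2.1 little to act on

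*Combined protocol and SAP*

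**What the plan says.** Section 8.3 gives three alternative routes to being evaluable for response, for anyone who received at least one dose:

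1. progression or death on protocol therapy;
2. at least one cycle on therapy, provided "the tumor is not removed surgically prior to the time complete response or partial response is confirmed";
3. a confirmed complete or partial response.

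The only explicit replacement rule in 8.3 covers patients who electively stop before completing the seven doses of cycle 1. The section closes by classing everyone else as a non-responder, without saying whether that includes patients who failed all three routes.

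Section 8.2 sets the Simon design: 9 patients in stage 1, stop at 0 responses; otherwise "accrual will continue until a total of 24 evaluable patients have been enrolled", with 3 or more responses counted as success.

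Section 8.2.1 defines the time-to-progression population: "Patients who are considered evaluable for response will be included in an analysis of time to progression". Its list of end points for follow-up includes "3) resection of measurable tumor". Only progression and death from treatment complications are events, so resection is a censoring point.

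On timing, section 3.5.1.5 images after every even cycle, and section 6.2.2 requires confirmation at least 4 weeks after response criteria are first met.

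**The concern.** Take a patient with stable disease on the scans after cycles 2 and 4 whose tumor is then removed. Route 1 fails because there was no progression or death on therapy, route 2 because of the surgery, and route 3 because no response was confirmed. Read literally, this patient is not evaluable, and accrual to 24 evaluable patients brings in another.

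The exclusion depends on outcome. A confirmed responder is kept by route 3 whatever surgery follows, so the rule removes only patients who have no confirmed response and who would otherwise count as non-responders. At stake are the primary response rate and the chance of declaring the agent effective under the null, in a design where three responses decide the result.

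The second consequence needs no assumption about how often surgery occurs. Because 8.2.1 takes its population from response evaluability, a resected stable-disease patient contributes no progression-free follow-up, although the censoring rule there seems written for exactly such a case.

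**Working it through.** **Inputs (section 8.2).** p0 = 0.05, p1 = 0.25, alpha limit 0.10, beta 0.10; stage 1 n = 9, stop at 0; total n = 24, success at 3 or more; stated early termination under the null 63%.

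**Reproducing the design.**
- Early termination at p0: 0.95^9 = 0.630.
- P(declare effective) = sum over x ≥ 1 of P(X1 = x | 9) × P(X2 ≥ 3 − x | 15).
- At p = 0.05: 0.2985 × 0.1710 + 0.0629 × 0.5367 + 0.0084 × 1 = 0.0510 + 0.0337 + 0.0084 = 0.0931.
- At p = 0.25 the same sum gives 0.9028.

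The plan's figures hold: type I error 0.093, power 0.903, early termination 63%. The margin below 0.10 is thin.

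**Effect of removing and replacing.** Let q be the share of all non-responders who are removed. The response rate among those counted becomes

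p / [p + (1 − p)(1 − q)].

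Putting in p = 0.05 and applying the same 0/9, 2/24 rule:

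| q (assumed) | counted rate | early termination | type I error |
|---|---|---|---|
| 0 | 0.0500 | 0.630 | 0.093 |
| 3% | 0.0515 | 0.622 | 0.099 |
| 5% | 0.0525 | 0.616 | 0.104 |
| 10% | 0.0552 | 0.600 | 0.116 |
| 20% | 0.0617 | 0.564 | 0.148 |

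The 0.10 limit is passed between q = 3% and q = 4% (0.102 at 4%).

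**Allowing for route 1.** Patients who progress or die on therapy stay evaluable, so q = (share of non-responders without progression first) × (share of those resected). Both factors are assumptions:
- Half progress first, 10% of the rest resected: q = 0.50 × 0.10 = 5%, type I error 0.104.
- 70% progress first, 10% of the rest resected: q = 0.30 × 0.10 = 3%, type I error 0.099.

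**Effect on an observed rate.** Three responses in 24 is 12.5%. With two such patients counted it is 3/26 = 11.5%; with four, 3/28 = 10.7%.

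**Who is left for the censoring rule.** Within the response-evaluable set, resection can censor mainly two groups: confirmed responders resected later, and patients in whom one measurable lesion is removed but the tumor as a whole is not. Among 24 evaluable patients, expected confirmed responders number 24 × 0.05 = 1.2 at the null and 24 × 0.25 = 6 at the target rate, and only those then resected would be censored.

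**The case against.** Several points on the other side have force.

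- **Scope.** A reader might infer that any patient resected before a confirmed response is lost. That is not so: route 1 keeps everyone with progression or death on therapy. This stands and limits q.
- **Replacement.** A reader might take replacement of resected patients as stated. It is inferred from the target of 24 evaluable patients. Stage 1 refers only to 9 patients, and the closing sentence of 8.3 can be read as keeping resected patients in as failures. This stands too, but under that reading the surgery clause has no effect on the response count. Two analysts could therefore form different primary denominators from the same data.
- **Truncated assessment.** Best response is judged over six cycles, so a patient resected after cycle 2 has an incomplete assessment, not a proven failure. If resection were unrelated to eventual response, the counted rate would be p(1 − q) / [p(1 − q) + (1 − p)(1 − q)] = p, and type I error would stay at 0.093. The table therefore shows the end of the range at which no would-be responder is among those removed. Even so, measured by confirmed response as the plan defines it, every removed patient lacks one.
- **Contradiction.** A reader might infer that 8.2.1 and 8.3 flatly contradict each other. They do not. Section 8.3 speaks of the tumor, 8.2.1 of measurable tumor, and up to five target lesions are allowed, so a partial resection may leave a patient evaluable and censored. The rule is nearly empty, not impossible.
- **Frequency.** Eligible patients have refractory or recurrent disease without known curative therapy, and no resection rate is given. Resections may be few or none. Surgery is, however, foreseen in both 8.2.1 and 8.3, and section 3.6 does not list it among barred concurrent treatments.

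**Conclusion.** The point holds in a limited form. Read literally, 8.3 makes non-evaluable those treated patients who are resected with stable disease or an unconfirmed response and without progression or death on therapy. With accrual to 24 evaluable patients, they appear to be back-filled. Compared with counting all treated patients, this can only raise the response rate.

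The size cannot be fixed from the documents. A conclusion that the trial's type I error exceeds 0.10 would go too far: that needs more than 3% of all non-responders to be removed, no would-be responders among them, and replacement as inferred. In the two route 1 examples, type I error falls on either side of the limit (0.099 and 0.104).

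For time to progression, a secondary and preliminary aim, the loss of follow-up from resected stable-disease patients follows from the text alone, provided they are non-evaluable as 8.3 literally reads.

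**What to change.** In 8.3, delete the surgery condition from route 2. State that treated patients resected without a confirmed complete or partial response are evaluable, count as non-responders and are not replaced. List resected unconfirmed partial responses separately.

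In 8.2.1, state that these patients stay in the time-to-progression analysis and are censored at resection, as its item (3) already provides.

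This takes about two sentences and changes no treatment, visit or sample size. With q = 0, the planned type I error of 0.093 is restored.

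The cost should be named. A true responder resected before confirmation would count as a failure. If 10% of responders at a 25% true rate were affected, the counted rate would be 0.25 × 0.90 = 0.225 and power would fall from 0.903 to 0.862. At 20% the counted rate would be 0.20 and power 0.805. That error is conservative, and the separate listing makes it visible.

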8.4 INHIBITION OF NR0B1 IN TUMOR TISSUE AND CHANGES IN GENE EXPRESSION SIGNATURE

It will be important to determine if mithramycin inhibits NR0B1 in at least a modest fraction of patients in order to confirm that the agent is correctly meeting its intended target. This will require that biopsies be obtained on subjects 18 years or older with accessible biopsy sites, at both pre-treatment as well as on treatment. Given that no more than 42 subjects are expected to enroll onto this study as a maximum, the accrual target for this endpoint will be based on no more than 50% of the maximum enrollment projected. This portion of the study will be conducted as a pilot using up to 20 evaluable subjects. With 20 subjects, there would be 90% power to detect a difference between an unacceptably low fraction with inhibition of 5% and a more modestly acceptable fraction of 25% using a one-sided 0.10 alpha level exact test for a binomial proportion. If only 12 patients are able to provide biopsy results at both times, there would be 90% power to detect a difference between 5% and 45% with inhibition. Thus, while up to 20 patients with paired biopsies would be desirable, as few as 12 patients with the complete evaluation would be adequate to address this to some degree.

Should less than 12 patients with evaluable tumor biopsies be available at the time the toxicity and response objectives are met, enrollment on this trial will continue for patients undergoing tumor biopsies until a minimum of 12 patients with tumor biopsies evaluable for analysis of NR0B1 inhibition have been enrolled. In order to be evaluable for analysis of NR0B1 inhibition, NR0B1 expression has to be present on the tumor biopsy obtained at baseline.

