1 INTRODUCTION

1.1 STUDY OBJECTIVES

1.1.1 Primary Objectives

- 1.1.1.1 Phase I portion of this study is to: determine the tolerability, toxicity, and recommended dose of mithramycin in children and adolescents with refractory extracranial solid tumors.
- 1.1.1.2 Phase II portion of this trial is to: determine the objective response rate (CR and PR) of Ewing sarcoma with EWS-FLI1 fusion transcript to mithramycin in children and adults using RECIST criteria when administered at 17.5 microgram/kg over 6 hours once daily for 7 days to be repeated every 28 days until unacceptable toxicity or disease progression. If the pediatric phase II dose of mithramycin differs from the adult phase II dose, the protocol will be amended to address accrual and response rate to mithramycin in children in a separate stratum.
- 1.1.1.3 Evaluate if mithramycin inhibits NR0B1 in tumor tissue, and determine changes in EWS/FLI1 gene expression signature by obtaining mandatory tumor biopsies pre treatment and at steady state on day +4 of treatment in patients \geq 18 years old with Ewing sarcoma and EWS/FLI1 fusion transcript and disease amenable to percutaneous biopsy (phase II).

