2.1.1.11 Eligibility criteria for mandatory serial tumor biopsies

- Age: ≥ 18 years old
- Ewing sarcoma with EWS-FLI1 fusion transcript
- Hematologic and coagulation parameters within 2 days prior to each biopsy: Normal PT/PTT with exception of lupus anticoagulant, platelets ≥75,000/mcL, peripheral ANC ≥750/mcL
- Willing to undergo biopsies, which will only be performed on tumors amenable to percutaneous biopsy ([Error! Reference source not found.](#))

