3 STUDY IMPLEMENTATION

3.1 STUDY DESIGN

This study will be conducted as a single institution, open label Phase I/II trial of mithramycin. The Phase I portion will be conducted in children and adolescents (12 months to \leq 17 years of age) with refractory extracranial solid tumors. The cohort at the recommended dose or MTD will be expanded up to 12 patients, and attempts will be made to enroll at least 6 patients that are \geq 12 years of age and 6 patients that are $<$ 12 years of age to gain experience with a broad age range of patients.

In the phase II portion of the trial the adult dose (17.5 mcg/kg/dose) will be administered to patients with measurable refractory or recurrent Ewing sarcoma and EWS-FLI1 fusion transcript to determine the objective response rate (CR and PR) to mithramycin using RECIST criteria. Initially this portion of the trial will be open to eligible participants \geq 18 years of age. Enrollment will be expanded to include children and adolescents once safety at this dose is determined. If the pediatric phase II dose of mithramycin differs from the adult phase II dose, the protocol will be amended to address accrual and response rate to mithramycin in children in a separate stratum.

The Phase I and Phase II portions of the protocol will enroll patients simultaneously.

Patients with ESFT enrolled on this study (phase II portion) who meet eligibility criteria for tumor biopsies will undergo mandatory tumor biopsies to assess EWS-FLI1 target blockade by mithramycin (see [Appendix 7: Studies to be performed on tumor tissue](#)).

Mithramycin will be administered intravenously over 6 hours once daily for 7 days to be repeated every 28 days. Patients may continue to receive mithramycin for as long as they tolerate drug (Sections [3.1.1](#) and [3.4](#)) and do not have progressive disease (Section [6.2](#)).

Patients on study will be closely monitored for the development of toxicity including regular physical examinations, blood pressure monitoring, laboratory evaluations, and physical examinations with particular attention to the development of any signs of bleeding. Patients will be admitted to the hospital for the first treatment cycle during administration of mithramycin in order to allow for close monitoring of toxicities.

Disease will be monitored after every even treatment cycle using appropriate imaging studies using RECIST criteria.

Correlative studies are described in Section [5](#).

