8 STATISTICAL CONSIDERATIONS

8.1 PHASE I PORTION

The phase I portion of this study will enroll patients in a standard 3 + 3 design as described in Section [Error! Reference source not found.](#). The cohort at the recommended dose or MTD will be expanded to 12 patients, and attempts will be made to enroll at least 6 patients that are ≥ 12 years of age and 6 patients that are < 12 years of age to gain experience with a broad age range of patients.

The maximum number of evaluable patients for this phase is 18 (6 patients at 2 dose levels and 6 to expand MTD to 12).

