8.6 NUMBER AND RATE OF ACCRUAL

If a maximum of 18 patients are required to complete the phase I portion, and 9 to 24 patients are required to complete the phase II portion, the maximum number of evaluable patients required to complete both portions of this trial is 42.

With an estimated monthly accrual of 1-2 patients, the projected duration of this study is 2 to 3.5 years.

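### Section 8.4 sets the 20-pair biopsy target against 42 patients, 18 of whom are too young to be biopsied, and misstates the power of 12 pairs at 45% inhibition (95.8%, not 90%)

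*Combined protocol and SAP*

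**What the plan says.** Section 1.1.1.3 makes the biopsy work a primary objective: "Evaluate if mithramycin inhibits NR0B1 in tumor tissue", using paired biopsies in adults with Ewing sarcoma in phase II.

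Section 8.4 takes 42 as the maximum enrolment and says that "the accrual target for this endpoint will be based on no more than 50% of the maximum enrollment projected". It then plans a pilot with up to 20 evaluable pairs. It states 90% power for 20 pairs, 5% versus 25%, with a one-sided 0.10 exact binomial test. For 12 pairs it says "there would be 90% power to detect a difference between 5% and 45% with inhibition". It treats 20 as desirable and 12 as adequate only in part. If fewer than 12 pairs exist when the other objectives are met, enrolment of biopsy patients continues until there are 12. For a pair to count, "NR0B1 expression has to be present on the tumor biopsy obtained at baseline".

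The make-up of the 42 and the age limits stand elsewhere:

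- Section 8.6: "the maximum number of evaluable patients required to complete both portions of this trial is 42", formed from 18 phase I and up to 24 phase II patients.
- Section 8.1: "The maximum number of evaluable patients for this phase is 18".
- Section 3.1: "The Phase I portion will be conducted in children and adolescents". Section 2.1.1.3 sets the upper age limit of phase I at 17.
- Section 2.1.1.11, on biopsy eligibility: "Age: ≥ 18 years old".
- Section 3.1.3 opens phase II to children once the adult dose is considered safe.
- Section 8.2 raises the accrual ceiling by two for the patients treated at 25 mcg/kg, and stops accrual if none of the first 9 patients responds.

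**The concern.** The sentence with 42 invites the reader to judge 20 pairs as a modest demand, just under half of the trial. The phase I patients in that denominator cannot supply a pair at any point. Measured against the patients who can, 20 pairs is a demanding target. The number that the plan protects is 12, so the power at 12 deserves an accurate statement. The figure given there does not follow from the stated test, and nothing is given for 12 pairs at 25%, the fraction that 8.4 uses to justify 20.

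What is at stake is how a sponsor or review board reads the prospects of a primary objective. The validity of the test is not in question.

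**Working it through.** **Inputs.** From 8.4: null 5%; alternatives 25% (20 pairs) and 45% (12 pairs); exact binomial test, one-sided 0.10; maximum enrolment 42; share at most 50%. From 8.1 and 8.6: 18 phase I and up to 24 phase II patients. From 8.2: two further phase II patients, and a stop after 0 responses in 9. The one-sided 0.10 level is stated for 20 pairs; I assume that it carries over to 12.

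**Step 1: the base.**

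- As stated: 50% of 42 = 21, and 20/42 = 47.6%.
- Patients who cannot be biopsied because of age: 18/42 = 42.9%.
- Remaining base: 42 − 18 = 24, or 24 + 2 = 26 if the two patients at 25 mcg/kg count. Section 8.2 excludes them from the response design only, and 8.4 is silent.
- Share needed for 20 pairs: 20/24 = 83.3%, or 20/26 = 76.9%.
- Children in phase II reduce the base. With 4 among 24 (6 among 26), exactly 20 adults remain and every one must give an evaluable pair. With 5 (7), 19 remain.

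The 24 counts patients evaluable for response. A patient replaced under 8.3 may still have given a pair, because the second biopsy is on about day 4 of cycle 1, so replacements could add a few. In the other direction, Appendix 7 rules out lung lesions and lets patients decline later biopsies, and 8.4 requires NR0B1 at baseline. The documents give no rates for these losses.

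**Step 2: the stage 1 stop.** At a true response rate of 5%, the probability of 0 responses in 9 is 0.95^9 = 0.630, which matches the 63% in 8.2. After such a stop, the only route to further pairs is the continuation rule, which runs to 12. The shares in step 1 therefore apply only if the trial goes on to 24.

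**Step 3: the power.** For n pairs and rejection at r or more,

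P(X ≥ r) = 1 − Σ (k = 0 to r − 1) C(n,k) p^k (1 − p)^(n−k),

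with r the smallest value for which this is at most 0.10 at p = 0.05.

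*20 pairs (the plan's figure first).* r = 2 has size 0.264, so r = 3, with size 0.0755. At 25%: 1 − (0.0032 + 0.0211 + 0.0669) = 0.909. The stated 90% reproduces.

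*12 pairs.* r = 2 has size 1 − (0.5404 + 0.3413) = 0.118, which is too large, so r = 3, with size 0.0196.

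- At 45%: 1 − (0.0008 + 0.0075 + 0.0339) = 0.958, against the stated 90%.
- At 25%: 1 − (0.0317 + 0.1267 + 0.2323) = 0.609.

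| Pairs | Reject at | Size | Power at 25% | Power at 45% | 90% power reached at |
|---|---|---|---|---|---|
| 12 | 3 or more | 0.020 | 60.9% | 95.8% | 38.6% |
| 19 | 3 or more | 0.067 | 88.9% | 99.9% | – |
| 20 | 3 or more | 0.076 | 90.9% | 99.9% | 24.5% |

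No number of pairs from 8 to 19 reaches 90% at 25%.

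**Step 4: can another method give 90% for 12 pairs at 45%?** The critical value is also 3 at one-sided 0.05 and 0.025. Rejecting at 4 or more gives 86.6%, and a randomised exact test gives 98.5%. Normal approximations, with and without continuity correction, give 94.9% to 98.7% over those three levels, and the arcsine approximation 94.2% to 98.8%. None comes within 2 points of 90%.

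**The case against.** The strongest reply is that nothing in the design rests on the sentence with 42. The figure of 20 is supported by power alone, the minimum of 12 is protected by the continuation rule, and 8.4 calls this part a pilot. The adult-only restriction appears in the sentence just before, so it is not hidden. The 12-pair figure is true if read as at least 90%. Moving the alternative from 25% to 45% already tells the reader that 12 pairs can detect only a large effect. All of this stands, and it is why the point is minor.

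Three stronger readings are tempting, and the documents do not support them.

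- A reader might infer that the 50% rule contradicts a target of 20, because half of 24 is 12. The rule is a cap on the whole projected enrolment. Half of 42 is 21, so 20 meets it as written. The base is badly chosen, but there is no contradiction.
- A reader might take 61% as a second failed reproduction. Section 8.4 states no power for 12 pairs at 25%, so there is no figure for it to contradict.
- A reader might take 83% as the share the trial will need in all circumstances. It applies only if phase II reaches 24, and it ignores children and replacements.

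What the reply does not remove is that the denominator includes 18 patients who are ineligible by age, and that one stated power does not follow from the stated test.

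**Conclusion.** The point holds, at minor severity. Twenty pairs needs about 83% of 24 phase II patients (77% of 26), not 48% of 42. The share of adults is larger if children enrol, and 20 is not reachable after a stage 1 stop. The 90% stated for 12 pairs at 45% should be 95.8%, so the plan errs on the cautious side there.

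The conclusion assumes that the same test applies at 12 pairs (the result does not change at one-sided 0.05 or 0.025) and that few replaced patients add pairs. Whether the two patients at 25 mcg/kg count moves the share between 77% and 83% without changing the conclusion.

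**What to change.** Change the wording of 8.4 only.

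1. Remove the sentence based on 42 and 50%, or restate the base as adult phase II patients.
2. Justify 20 by power: reject at 3 or more of 20, size 0.076, power 91% at 25%, the smallest number of pairs that reaches 90%. Add that it needs evaluable pairs from about 83% of 24 (77% of 26) patients if the trial completes stage 2, a larger share of the adults if children enrol, and that it is not reachable after a stage 1 stop.
3. Restate the 12-pair power: reject at 3 or more of 12, size 0.020, power 96% at 45%, 90% at about 39%, 61% at 25%.

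An intermediate row is optional: 16 pairs, reject at 3 or more, size 0.043, power 80% at 25%.

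Keep the test, the minimum of 12 and the continuation rule. Accrual and eligibility do not change. The cost is that the prospects for 20 pairs, and the power of 12 pairs at 25%, will look less favourable than 8.4 now suggests, while the 12-pair power at 45% rises from 90% to 96%.
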